## **6.5. Follow-Up**

### **6.5.1. Safety Follow-Up**

The safety follow-up period is the interval between the EOT visit and the scheduled follow-up visit, which should occur 30 to 35 days after the EOT visit (or after the last dose of study drug if the EOT visit was not performed). Adverse events and SAEs must be reported up until at least 30 days after the last dose of study drug, the date of the follow-up visit, or until toxicities resolve, return to baseline, or are deemed irreversible, whichever is longer. Reasonable efforts should be made to have the subject return for the follow-up visit and report any AEs that may occur during this period. If the subject cannot return to the site for the safety follow-up visit (eg, lives far away), then the subject should be contacted by telephone for assessment of AEs and SAEs. Sites must document this contact in the source.

Subjects are required to remain on PJP prophylaxis for at least 2 to 6 months after the last dose of study drug (see Section 5.7.1) and should be reminded of this at the safety follow-up visit. Sites should follow up with subjects to confirm that they have been compliant with the prophylactic treatment for the duration of this period.

### **6.5.2. Survival Follow-Up**

Once a subject has received the last dose of study drug, the subject moves into the survival follow-up period and should be contacted by telephone, email, or visit at least every 12 weeks to assess for subsequent MF treatments and survival status until death, withdrawal of consent, or end of study (EOS), whichever occurs first.

## **6.6. End of Study**

The EOS will occur when the last enrolled/randomized subject has completed the follow-up visit.

## **6.7. Unscheduled Visits**

Unscheduled visits may be held at any time at the investigator's discretion, and appropriate clinical and laboratory measurements may be performed based on AEs or other findings.

## **7. CONDUCT OF STUDY ASSESSMENTS AND PROCEDURES**

### **7.1. Administration of Informed Consent Form**

Valid informed consent must be obtained from the study subject before conducting any study-specific procedures using an ICF approved by the local IRB/IEC that contains all elements required by ICH E6 and describes the nature, scope, and possible consequences of the study in a form understandable to the study subject. Local and institutional guidelines for ICF content and administration must be followed; the original signed ICF must be retained by the investigator, and a copy of the signed ICF must be provided to the study subject. The informed consent process for each subject must be documented in writing within the subject source documentation.

### **7.2. Interactive Web Response System Procedure**

The IWRS will be accessed to obtain a subject ID number when a subject enters the screening portion. Upon determining that the subject is eligible for study entry, and using the screening ECOG score, the IWRS will be contacted to obtain treatment group and study drug assignment. Additionally, the IWRS will be contacted at each regular study visit to update the study drug supply. Full details will be provided in the IWRS manual.

### **7.3. Demography and Medical History**

#### **7.3.1. Demographics and General Medical History**

Demographic data will be collected at screening, including age, sex, race, and ethnicity. A complete medical history will be obtained.

#### **7.3.2. Disease Characteristics and Treatment History**

A disease-targeted medical and medication history will be collected at screening. Date of MF diagnosis and prior bone marrow biopsy data as to fibrosis stage will be recorded. All treatments for MF, including a complete history of ruxolitinib usage, will be recorded.

#### **7.3.3. Transfusion History Status**

All transfusions of RBC products or platelets from at least 16 weeks before the screening visit will be recorded. The product(s) delivered, date of transfusion, and units delivered will be recorded on the CRF.

#### **7.3.4. Screening Symptom Form**

In order to satisfy inclusion Criterion 4, active symptoms of MF at the screening visit as demonstrated by presence of 1 symptom score  $\geq 5$  or 2 symptom scores  $\geq 3$  using the Screening Symptom Form ([Appendix D](#)) will be recorded on the CRF.

## **7.4. Prior and Concomitant Medications and Procedures**

Prior and concomitant medications and procedures will be reviewed to determine subject eligibility. All concomitant medications and measures must be recorded in the CRF, and any medication received or procedure performed within 30 days before the first dose of INCB050465 and up to the end of study will be recorded in the CRF. The medication record will be maintained after signing the ICF to document concomitant medications, including any changes to the dose or regimen. Concomitant medications include any prescription, over-the-counter, or natural/herbal preparations taken or administered during the study period. Concomitant treatments and/or procedures that are required to manage a subject's medical condition during the study will also be recorded in the CRF.

## **7.5. Safety Assessments**

### **7.5.1. Adverse Events**

Adverse events will be monitored from the time the subject signs the ICF. Subjects will be instructed to report all AEs during the study and will be assessed for the occurrence of AEs throughout the study. In order to avoid bias in eliciting AEs, subjects will be asked general, nonleading questions such as "How are you feeling?" All AEs (serious and nonserious) must be recorded on the source documents and CRFs regardless of the assumption of a causal relationship with the study drug. The definition, reporting, and recording requirements for AEs are described in Section 8.

### **7.5.2. Physical Examinations**

Clinically notable abnormalities that are considered clinically significant in the judgment of the investigator are to be reported as AEs.

Physical examinations must be performed by a medically qualified individual such as a licensed physician, physician's assistant, or an advanced registered nurse practitioner, as local law permits.

Clinically notable abnormalities that are considered clinically significant in the judgment of the investigator are to be reported as AEs.

#### **7.5.2.1. Comprehensive Physical Examination**

The comprehensive physical examination will include height (at screening) and body weight and assessment(s) of the following organ or body systems: skin; head, eyes, ears, nose, and throat; thyroid; lungs; cardiovascular system; abdomen (liver, spleen); extremities; and lymph nodes; as well as a brief neurological examination. The comprehensive physical examination should also include an assessment of body fluid abnormalities including ascites and edema.

### **7.5.2.2. Targeted Physical Examination**

A targeted physical examination will be a symptom-directed evaluation and will include assessment(s) of the body systems or organs, as indicated by subject symptoms, AEs, or other findings as determined by the investigator or designee. A targeted physical examination must include a measurement of the subject's body weight (within 1 lb. or 0.5 kg), including an assessment of body fluid abnormalities of edema and ascites, and an evaluation of any AEs or symptoms that the subject has had previously.

### **7.5.3. Vital Signs**

Vital sign measurements include blood pressure, pulse, respiratory rate, and body temperature. Blood pressure and pulse will be taken with the subject in the recumbent, semirecumbent, or sitting position after 5 minutes of rest. Clinically notable abnormalities that are considered clinically significant in the judgment of the investigator are to be reported as AEs.

### **7.5.4. Electrocardiograms**

All 12-lead ECGs will be performed with the subject in a recumbent or semi recumbent position after 5 minutes of rest. Electrocardiograms will be performed at the screening visit, Week 24 and the EOT visits, or as clinically indicated at investigator discretion.

The 12-lead ECGs will be interpreted by the investigator at the site to be used for immediate subject management. The decision to include or exclude a subject or withdraw a subject from the study based on an ECG flagged as "Abnormal, Clinically Significant" is the responsibility of the investigator, in consultation with the sponsor's medical monitor, as appropriate. Clinically notable abnormalities relative to the screening ECG that are considered clinically significant in the judgment of the investigator are to be reported as AEs.

## **7.6. Efficacy Assessments**

### **7.6.1. Bone Marrow Biopsy**

Bone marrow biopsy (and additional aspirate collection) will be collected at screening, at Week 24, and every 24 weeks thereafter. Subjects without circulating blasts at the screening hematology assessment may use a historical biopsy obtained within the 2 months before screening, and all data and reports are available for investigator's review. The previous data will need to be entered into the CRF for this study, with explanation as to the origin of the data (date of biopsy/aspirate). Subjects without a previous biopsy report as indicated above must have a biopsy at screening or baseline or they will not be able to enroll in the study. Collection, processing, and staining of bone marrow samples will be performed in accordance with standard procedures at the investigative sites. The bone marrow biopsy and optional aspirate should be assessed by an experienced hematopathologist using his/her standard examination. Samples of bone marrow biopsy and aspirate will be sent to Incyte or its designee for additional immune and molecular profiling.

### **7.6.2. Spleen Palpation**

Spleen length will be assessed by manual palpation at every study visit (laboratory-only visits not included) and will be used for routine subject management. Investigators will be provided with a soft centimeter ruler so that palpable spleen length is measured in centimeters and not in finger breadths. The edge of the spleen shall be determined by palpation and measured in centimeters, using a soft ruler, from the costal margin to the point of greatest splenic protrusion. Spleen length must be recorded on the CRF.

### **7.6.3. Imaging**

The primary measure of spleen size will be by MRI (or CT scan in applicable subjects). An MRI of the upper and lower abdomen and pelvis will be performed at baseline, Week 12 and Week 24, and every 12 weeks thereafter through Week 108. An MRI will be performed with a body coil because the objective is to measure organ volume, not to find very small lesions. The MRIs will be read initially by local radiologists who will assess the scan for quality and send all scans (MRI or CT) to the central imaging laboratory the same day, if at all possible. The scans from an individual subject will be read by a central reader. Spleen and liver volume will be obtained by outlining the circumference of the organ and determining the volume using the validated technique of least squares. The MRI will not determine spleen length below the costal margin, as there are no validated approaches for determining this measurement. Procedure-specific training for scanning and image capture will be provided by the vendor.

An MRI is the preferred method for obtaining spleen volume data. However, CT scans may be performed at the visits where MRI is designated if the subject is not a candidate for MRI (eg, because of the presence of metal clips in the body, because of claustrophobia) or if MRI is not readily available. CT scans will be similarly processed by the same central laboratory as used for MRIs. Procedure-specific training for scanning and image capture will be provided by the vendor. NOTE: The same method (MRI vs CT) must be used for all visits for a given subject unless a new contraindication to the use of MRI occurs (eg, pacemaker insertion).

### **7.6.4. Symptom Diary**

Symptoms of MF will be assessed using a symptom diary (modified MFSAF v3.0 diary; [Appendix E](#)). Subjects will be issued a hand-held device on which to record answers to queries regarding MF symptoms. Symptoms assessed will include filling up quickly/early satiety, abdominal discomfort, abdominal pain, inactivity, night sweats, itching, and bone/muscle pain. The modified MFSAF v3.0 diary will be completed by subjects each night beginning at Day -7 (first day of baseline) and continuing to the Week 24 visit (25 weeks total). Subjects will bring the device to the study site at study visits on Day 1 and Weeks 4, 8, 12, 16, and 20, so that the device charging can be verified and the accumulated data can be downloaded. NOTE: Subjects who will have overnight stays associated with their study visit must also bring their docking station so that their device can be fully charged at all times and so that they can complete the evening diary entries. The device will then be returned to the subject at these same visits for continued use each night. The subject will return the device and the docking station for the final time at the Week 24 visit so that the data can be archived. Detailed directions for the administration of the modified MFSAF v3.0 diary will be provided in a reference manual. French and Spanish translations of the modified MFSAF v3.0 diary will be available.

### **7.6.5. Myeloproliferative Neoplasms Symptom Assessment Form**

The MPN-SAF ([Emanuel et al 2012](#); [Appendix F](#)) will be completed by subjects at the study visits noted in [Table 8](#).

### **7.6.6. Eastern Cooperative Oncology Group Status**

Eastern Cooperative Oncology Group performance scores (see [Appendix G](#)) will be required at screening to evaluate eligibility and stratification category and will be assessed at other study visits noted in [Table 8](#).

### **7.6.7. Patient Global Impression of Change**

The PGIC will be administered at each visit beginning with Week 4 and consists of a single question to which the subject answers on a scale of 1 to 7. See [Appendix H](#).

### **7.6.8. IWG-MRT Assessment**

Overall response assessment will be graded according to the IWG consensus criteria for treatment response in PMF, PPV-MF, and PET-MF ([Tefferi et al 2013](#)). International Working Group–MRT assessment will be performed at Week 24 and every 24 weeks thereafter as per [Table 8](#). Recently published response criteria developed by the IWG on MF will be utilized in this study ([Tefferi et al 2013](#)) and are defined as described in [Appendix I](#).

## **7.7. Laboratory Assessments**

Refer to [Table 9](#) and [Table 10](#) for the schedule of laboratory assessments and the laboratory tests that will be performed. All blood draws for laboratory assessments will be performed before administration of INCB050465 or morning ruxolitinib dose.

### **7.7.1. Chemistry**

Serum chemistries will be performed by the local laboratory using institutional best practices. Results and normal reference ranges will be entered onto the CRF.

### **7.7.2. Hematology**

Hematology assessments including complete blood count with differential will be performed at the local laboratory using institutional best practices. Results and normal reference ranges will be entered onto the CRF.

### **7.7.3. Urinalysis**

Urinalysis will be performed by a central laboratory.

### **7.7.4. Coagulation**

Coagulation parameters will be determined at the local laboratory using institutional best practices. Results and normal reference ranges will be entered onto the CRF.

### **7.7.5. Lipid Panel**

Lipid panel will be performed on samples collected at screening, at Weeks 12 and 24, and every 12 weeks thereafter. Subjects must arrive for this blood collection after an overnight fast of at least 12 hours. These assessments will be performed by the central laboratory.

### **7.7.6. Pregnancy Testing**

A serum pregnancy test will be required for all women of childbearing potential during screening) and at the end of treatment visit. This assessment will be performed by the central laboratory. Urine pregnancy tests will be conducted as outlined in [Table 9](#), as medically indicated or per country-specific requirement. Urine pregnancy tests will be performed locally. If a urine pregnancy test is positive, then the results should be confirmed with a serum pregnancy test.

If the serum pregnancy test is negative after a urine test was positive, then the investigator will assess the potential benefit/risk to the subject and determine whether it is in the subject's best interest to resume study drug and continue participation in the study.

Follicle-stimulating hormone levels will be determined only at screening to verify hormonal menopause in relevant subjects.

### **7.7.7. Serology**

Serology will be performed by the central laboratory. Serology will include HBV DNA and HCV RNA measurement, hepatitis B surface antigen, anti-hepatitis B core antibody, CMV DNA, and HIV testing.

## **7.8. Pharmacokinetic Assessments**

[figure not shown]
### **7.8.1. Blood Sample Collection**

Pharmacokinetic sampling will occur on 3 separate days in Part 1, Part 2, Part 3, and Part 4 of the study (see [Table 11](#) for timing of PK samples). The Laboratory Manual will describe sample collection and shipping to the central laboratory, where samples will be held until processing.

### **7.8.2. Bioanalytical Methodology and Analysis**

The plasma samples will be analyzed for INCB050465 and/or ruxolitinib using validated liquid chromatography tandem-mass spectrometry methods. Day 1 samples will be analyzed for INCB050465 only; Week 2 samples will be analyzed for ruxolitinib only; Week 4 samples will be analyzed for both INCB050465 and ruxolitinib. The plasma samples may also be used for incurred sample reanalysis to ensure data quality.

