#### **2.1.2. Secondary Objectives**

- To evaluate the efficacy of INCB050465 in combination with ruxolitinib on subject reports of MF symptoms.
- To evaluate the efficacy of INCB050465 in combination with ruxolitinib on response using International Working Group (IWG)–Myeloproliferative Neoplasms Research and Treatment (MRT) criteria.
- To assess the PK of INCB050465 and ruxolitinib alone and when given in combination in subjects with MF.
- To evaluate the safety and tolerability of INCB050465 when combined with ruxolitinib in subjects with MF.

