**Table 11: Schedule of Pharmacokinetic Sampling for Part 1, Part 2, Part 3, and Part 4**

Study Day 1	Week 2	Week 4

Subject arrives having withheld both INCB050465 and ruxolitiniba
 
Predose sample = Time 0 sample
 
Administer ruxolitinib
 
Timed samplesb:
 
 
1 hour postdose
 
2 hour postdosec
 
4 hour postdose
 
 
Administer INCB050465
	
Subject arrives having withheld both INCB050465 and ruxolitiniba
 
Predose sample = Time 0 sample
 
Administer INCB050465
 
Timed samplesb:
 
 
1 hour postdose
 
2 hour postdosec
 
4 hour postdose
 
 
Administer ruxolitinib
	
Subject arrives having withheld both INCB050465 and ruxolitiniba
 
Predose sample = Time 0 sample
 
Administer INCB050465 plus ruxolitinib
 
Timed samplesb:
 
 
1 hour postdose
 
2 hour postdosec
 
4 hour postdose
 

a Subjects are also to arrive at the study visits in the fasted state.

b Window for 1-, 2-, and 4-hour collections is  $\pm$  15 minutes.

c Subjects may eat after the 2-hour timepoint sample has been drawn.

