## 6.3. Treatment

The treatment period begins with the first dose of INCB050465 (Day 1) through the point at which the investigator determines the subject will be permanently discontinued from study drug.

There will be study visits and laboratory-only visits in the study. [Table 8](#), [Table 9](#), and [Table 10](#) provide the scheduled assessments for each study visit and laboratory-only visit.

Subjects will have a regularly scheduled study visit at screening, baseline, Day 1, and after 4, 8, 12, 16, 20, and 24 weeks of treatment (ie, visits designated Week 4, Week 8, Week 12, Week 16, Week 20, and Week 24) and then every 12 weeks thereafter if continuing on treatment, where blood samples, spleen measurements, and other assessments will be obtained. There is also a

study visit at the end of 2 weeks treatment (designated visit Week 2) for PK sampling, AE assessment and hematology blood draws. The visit window is  $\pm$  5 days for visits through Week 24 and  $\pm$  7 days for visits in the extension portion. The timing for study visits will be based on the date of the Day 1 visit when treatment with INCB050465 is initiated.

All serology, lipid profile, and urinalysis laboratory assessments collected at the visits in [Table 9](#) will be analyzed by a central laboratory. Serum chemistry, hematology, and coagulation parameters will be assessed using local laboratories. Where needed, urine pregnancy will be assessed by local lab. Bone marrow biopsy samples will be assessed for MF characteristics by local lab; subsequent studies using remaining material will be conducted by sponsor or its designee. [REDACTED] PK samples will be collected and analyzed by the sponsor or sponsor's designee. Subjects will arrive for all study visits (including Week 2, not at laboratory-only visits) having withheld the morning dose of ruxolitinib and INCB050465 and in the fasted state; administration will occur in the clinic (first 24 weeks only). Subjects should be told to bring a snack or small meal to the study visits, as they will arrive for the visits in the fasted state.

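### Protocol Section 7.8.2 assigns the wrong analyte to the Day 1 and Week 2 PK samples, so neither drug-alone profile would be measured

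*Protocol*

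**What the plan says.** Section 7.8.2 of the Protocol allocates analytes by visit: "Day 1 samples will be analyzed for INCB050465 only; Week 2 samples will be analyzed for ruxolitinib only". For the third PK visit it adds: "Week 4 samples will be analyzed for both INCB050465 and ruxolitinib".

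Table 11 sets the order of dosing and sampling. At all three visits the starting state is the same: "Subject arrives having withheld both INCB050465 and ruxolitinib". A predose sample is taken, and then:

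- Day 1: the first step is "Administer ruxolitinib", followed by samples at 1, 2 and 4 hours. INCB050465 is the last step.
- Week 2: the first step is "Administer INCB050465", followed by samples at 1, 2 and 4 hours. Ruxolitinib is the last step.
- Week 4: "Administer INCB050465 plus ruxolitinib", followed by samples at 1, 2 and 4 hours.

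The purpose is stated in Section 2.1.2: "To assess the PK of INCB050465 and ruxolitinib alone and when given in combination in subjects with MF". Section 2.2.2 repeats this as an endpoint, and Section 9.4.3 plans summaries of Cmax and AUC for each drug on both footings.

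**The concern.** The three-visit layout of Table 11 isolates one drug at a time and then combines them. Day 1 captures ruxolitinib before any INCB050465 exposure. Week 2 captures INCB050465 with no ruxolitinib that morning. Week 4 captures both. Section 7.8.2 names, for each of the first two visits, the drug that is given only after the last sample has been drawn.

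If the laboratory follows that sentence, Day 1 yields INCB050465 results that are blank by design, and Week 2 yields the tail of the previous evening's ruxolitinib dose. The comparison of each drug alone with the combination, which is the reason for having three PK days, cannot be made.

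**Working it through.** No power or error-rate calculation is involved. The check sets the dosing order against the assay instruction and counts the usable samples.

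**Inputs**
- Samples per PK visit: predose, 1, 2 and 4 hours, so 4 (Table 11).
- PK days: Day 1, Week 2 and Week 4 only (Table 9 note; Section 7.8.1 confirms three days).
- First INCB050465 dose: Day 1 (Protocol Section 6.3; SAP Section 4.1.1). Earlier PI3K inhibitor therapy is excluded (exclusion criterion 15).
- Last ruxolitinib dose before the Week 2 samples: the previous evening (Section 7.10.1). Doses are about 12 hours apart (Section 5.3.2.1).

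**Side by side**

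| Visit | Drug given before the timed samples | Drug given after the last sample | Analyte in 7.8.2 | Samples assayed for the drug just given |
|---|---|---|---|---|
| Day 1 | ruxolitinib | INCB050465 (first ever dose) | INCB050465 | 0 of 4 |
| Week 2 | INCB050465 | ruxolitinib | ruxolitinib | 0 of 4 |
| Week 4 | both | none | both | 4 of 4 for each drug |

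**Day 1.** All four samples precede the subject's first INCB050465 dose. An INCB050465 assay has nothing to measure. The ruxolitinib-alone profile is in the tube but is not assayed.

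**Week 2.** If the evening ruxolitinib dose was taken about 12 hours before the predose sample (an assumption from the dosing interval), the samples fall at about 12, 12 + 1 = 13, 12 + 2 = 14 and 12 + 4 = 16 hours after that dose. They give a residual trough with no post-dose profile. They also come after about two weeks of INCB050465, so they are not ruxolitinib alone. The post-dose INCB050465 profile is in the tube but is not assayed.

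**Profiles obtained.** As written: drug-alone 0 of 2, combination 2 of 2. With the Day 1 and Week 2 analytes exchanged: drug-alone 2 of 2, combination 2 of 2, from the same samples.

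**Number of samples.** Protocol Section 4.3.1 gives 10 enrolled in Part 1, 20 enrolled in Part 2, about 5 expected in Part 3 and about 55 planned in Part 4: 10 + 20 + 5 + 55 = 90. At 4 samples per visit, 90 × 4 = 360 Day 1 samples and 360 Week 2 samples. Counting only the 10 + 20 = 30 subjects stated as already enrolled, 30 × 4 = 120 per visit with full attendance. SAP Section 10.2.3 records that enrollment ended early, so 360 is best read as an upper figure.

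**Could other data fill the gap?** No other visit has PK sampling. The SAP (Section 1) sends population PK to a separate report, but a model cannot supply ruxolitinib concentrations before INCB050465 exposure if none was assayed. SAP Section 10.1 lists no change to protocol-defined analyses.

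**The case against.** The contradiction itself is hard to dispute: both texts are current, and neither a redaction nor the amendment log explains it. The arguments are about how much it matters.

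- **The laboratory may have done it correctly.** Section 7.8.1 refers to a Laboratory Manual, which is not among the documents. It may hold the right assignment, and blank Day 1 results would be noticed. This stands as a caution: the documents show what was instructed, not what was run. The Protocol sentence still needs correcting.
- **Only a descriptive secondary analysis is affected.** The primary endpoint, the interim rule and the Week 4 combination PK do not depend on it. That is true. But following the text loses the drug-alone half of a stated objective, and preventing this costs almost nothing.
- **The Week 2 profile is not pure monotherapy.** Some ruxolitinib from the evening before may remain, and sampling stops at 4 hours, so any AUC is partial. Both limits belong to the design and remain after the correction.
- **A Week 2 ruxolitinib reading might be intended**, since the reminder cards record the previous evening's dose time for Weeks 2 and 4. That could support a residual reading. It cannot justify assaying Day 1 plasma for a drug never taken, or omitting INCB050465 at Week 2.
- **The error could lie in Table 11 instead.** This is less likely. Day 1 is the only PK visit without INCB050465 on board, so it is the only possible source of ruxolitinib-alone data, and the table's sequence fits the objective.

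**Conclusion.** The concern holds. Section 7.8.2 and Table 11 contradict each other, and following Section 7.8.2 gives no post-dose drug-alone profile for either drug in any subject. Per subject, 4 Day 1 and 4 Week 2 samples are assigned to the wrong analyte, or up to about 360 per visit on planned or enrolled numbers. The per-subject conclusion does not depend on final enrollment.

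It rests on reading the steps in Table 11 in the order listed, which the Week 2 column mirrors, and on Day 1 being the first INCB050465 dose, which both documents state. At Week 2, alone means no ruxolitinib that morning. The fault is a drafting inconsistency in the assay instruction; the sampling design can serve the objective. It must be corrected before drug-alone PK is assayed or reported.

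**What to change.** In Protocol Section 7.8.2, exchange the two analytes: assay Day 1 samples for ruxolitinib only and Week 2 samples for INCB050465 only, and leave Week 4 as both. Check the Laboratory Manual and bring it into line if it repeats the error.

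Confirm from the assay records which analytes were run. If samples were processed as written, re-assay retained plasma for the correct drug, provided that enough remains and is still within its stability period; the documents give neither. Otherwise, state in the PK report that the drug-alone profiles were not obtained and make no alone-versus-combination comparison.

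The cost is one sentence in the Protocol, with a matching check of the manual. Dosing, blood draws, sampling times and the number of assays do not change. Extra laboratory cost arises only if a re-assay is needed.
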